5.3 Missing data

Missing data on covariates will be handled using formal multiple imputation as needed (Little 2002; 1992; Molenberghs 2007). The proposed mixed effects models make limited assumptions of "missing at random" (MAR). To the extent that children are lost to follow-up, we shall include in our models covariates that are associated with the probability of dropout, to limit confounding by dropout. We anticipate no school withdrawals. The primary analysis will be "as randomized" (also called intention to treat). Reporting will follow the CONSORT guidelines for randomized studies and cluster randomized designs. (Altman 2012; Elbourne and Campbell 2001).

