5.1 Specific Aim 1. Compare the effectiveness of all combinations of clinic and schoolbased interventions to improve asthma control and reduce symptom days. We have selected a factorial design because of its enhanced statistical power and its ability to estimate contrasts of interest, even within the framework of a cluster randomized design. Chakraborty (2009). Collins (2014). The added complexity of a conventional within-school randomization (child-level intervention) crossed with cluster-randomization (school-level intervention) can be handled with the proposed model alternatives, each with a different set of assumptions, to demonstrate the robustness of the findings to model specification. (Peters 2003). Our statistical methods will also estimate variation across schools in the effect over time. (Fitzmaurice, Laird, & Ware, 2011; Gelman & Hill 2007; Hayes & Moulton, 2017).

We propose and pre-specify three alternative approaches, each of which has been used in conventional cluster randomized design. Each approach has assumptions, strengths, and weaknesses. We intend to report the results of all three approaches, provided that models will converge to results, in order to assess robustness of findings to model choice. We do not consider use of the three approaches to be multiple comparisons. Rather, we consider the use of multiple approaches to assess this additional component of variability.

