5.1.3 Patient-level analysis – marginal models

Second, marginal models using generalized estimating equations (Fitzmaurice 2011) will produce robust estimates that adjust for clustering at the school level. These methods tend to be robust for

non-continuous outcomes (non-identify link models) and those outcomes will likely apply to our outcomes of asthma control (possibly a log gamma model) and number of symptom days (possibly a log link Poisson or negative binomial model). In contrast to mixed effects models, marginal models do not rely on numerical integration. In addition to generalized estimating equations, quasi-least squares regression (Shults and Hilbe, 2014) will also be implemented. Quasi-least squares regression is an approach for estimation of the correlation parameters that is in the framework of generalized estimating equations; it allows for application of correlation structures that were previously unavailable for generalized estimating equations and can sometimes be implemented when generalized estimating equations fails to converge.

Marginal models tend to work poorly for designs with small numbers of clusters. In our case, the number of clusters (36) is relatively large. Nevertheless, we shall implement at least one method for adjusting for a number of clusters that is not large, as implemented in Stata's program xtgeebcv program (Gallis 2019) and R's program "saws" (Fay and Graubard 2001).

5.1.4 School-level analysis -- randomization-test-based methods.

Third, assumption-free, randomization-test-based (permutation test) methods that do not rely on assumptions of parametric models will also be applied. (Berger, 2000; Good, 2005; Small, 2008; Tang 2009; Rosenbaum 2002). (Also see Hayes and Moulton 2017)

We will use conventional levels of statistical significance (p=0.05) for all pre-specified comparisons for these aims. We shall not apply Bonferroni corrections for estimates from different modeling methods that use the same specification.

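### The school-clustered GEE has no planned protection against dropout that depends on earlier ACQ scores, so a disagreement with the mixed model could not be read as model sensitivity

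*SAP*

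**What the plan says.** SAP section 5.3 gives the missing-data plan. On outcomes it says "The proposed mixed effects models make limited assumptions of" MAR, and it makes no such statement for the other two approaches. Imputation is for predictors: "Missing data on covariates will be handled using formal multiple imputation as needed". The remedy for dropout is "To the extent that children are lost to follow-up, we shall include in our models covariates that are associated with the probability of dropout". Section 5.4 adds that data up to dropout are kept and used.

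Section 5.1.3 describes the second approach: "marginal models using generalized estimating equations (Fitzmaurice 2011) will produce robust estimates that adjust for clustering at the school level". It adds quasi-least squares, of which it says "it allows for application of correlation structures that were previously unavailable for generalized estimating equations", but it chooses no structure for either method.

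Section 5.1.4 plans permutation tests and gives no method for missing outcomes.

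The response model in section 5.1.2 is weighted. Those weights come from a multinomial model for treatment group and address covariate imbalance, not dropout.

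On standing, section 5.1 says "We propose and pre-specify three alternative approaches, each of which has been used in conventional cluster randomized design" and "We intend to report the results of all three approaches". None is named primary. Agreement among them is the SAP's check of robustness to model choice.

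**The concern.** A likelihood-based mixed model with a correct covariance uses each child's earlier ACQ scores to allow for the scores that are missing. It therefore tolerates dropout that depends on those earlier scores. A GEE does so only if its mean model contains whatever drives dropout, if its working correlation correctly links a child's visits, or if it is weighted or run on imputed outcomes. The SAP commits to the first of these and leaves the others open.

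If children with poor recent control leave more often in one arm than in the other, the GEE and the mixed model would target different things at month 12, where dropout has accumulated. Protocol section 6.3.2 places the primary endpoint there (change from Study Visit 1 to Study Visit 5). A reader following the SAP would take the disagreement as sensitivity to model form when it came from the handling of dropout, and the SAP has no rule for telling the two apart.

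Dropout that differs by arm is plausible but not established. Under protocol sections 3.1 and 3.1.3, the primary-care arm has CHW contact at home and in clinic, while controls give their 3-, 6- and 9-month data by phone or in person.

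**Working it through.** **Inputs from the documents.** Loss: protocol section 3.3.2 expects at least 600 evaluable of 640, so (640 − 600)/640 = 6.25%. SAP section 8: 36 schools of 12 children (432), ICC 0.06, effects of 0.35 sd (A, child level) and 0.5 sd (S, school level). SAP section 5.5: 0.5 sd equals 0.4 ACQ units, so 1 sd is 0.8 units.

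**The plan's own figures.** The SAP gives none for dropout bias. The nearby planning figures can be reproduced:
- Design effect: 1 + 11 × 0.06 = 1.66, as stated.
- Power for A+ v A− at n = 432: 0.35/√(2/216) = 3.64; 3.64 − 1.96 = 1.68; power 0.953 (stated 0.95).

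**Mechanism.** GEE solves Σ D′V⁻¹(Y − μ) = 0 over observed visits. If V treats a child's visits as nearly unrelated, the month-12 terms compare only the children still present. When presence depends on the month-9 score, E(Y₁₂ | present, arm) differs from E(Y₁₂ | arm). The contrast is biased by the difference between arms in that shift, so a common mechanism nearly cancels. A V that correctly links a child's visits uses the earlier residuals to correct for the loss.

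**Simulation.** 4,000 schools × 12 children, ACQ at months 0, 3, 6, 9 and 12, month-12 effects A = −0.35 and S = −0.5 sd, school variance 0.06. Assumed, not in the documents: child variance 0.50, residual variance 0.44, one baseline covariate, monotone dropout, log-odds slope of 1 per sd of the last ACQ, and loss of 6.25%, 20% or 30%. Monte Carlo error is about 0.01 to 0.02. The last column is generalised least squares with the correct school-plus-child covariance, standing in for the mixed model.

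Bias in the month-12 A effect (sd):

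| Dropout depends on last ACQ | Loss | GEE, exchangeable in school | Same, plus baseline covariate | Correct covariance |
|---|---|---|---|---|
| in A− only | 6.25% | +0.029 | +0.021 | −0.010 |
| in A− only | 20% | +0.124 | +0.104 | +0.003 |
| in A− only | 30% | +0.172 | +0.144 | +0.003 |
| opposite directions by arm | 6.25% | −0.077 | −0.065 | −0.009 |
| opposite directions by arm | 20% | −0.215 | −0.185 | +0.006 |
| opposite directions by arm | 30% | −0.327 | −0.275 | +0.004 |

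An independence working correlation gave slightly larger bias (+0.033 and −0.086 at 6.25%). Two mechanisms did little harm. With dropout driven only by a baseline covariate in the model, GEE bias was −0.011 to +0.004. With the same dependence on last ACQ in both arms it was at most about 0.02.

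A second simulation with a weaker slope (0.5), no true effect and serial correlation 0.75 gave about 0.02 sd at 6% loss, 0.05 to 0.10 at 19% and 0.13 to 0.19 at 36%.

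**Remedy.** In 8,000 schools × 12, each visit's probability of being observed was modelled by logistic regression on last ACQ, arm, their product, school arm and the covariate. The weight is the product of 1/p over visits. Month-12 A effect, independence estimation:

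| Mechanism, loss | Full data | No dropout weights | Plus baseline ACQ and covariate | Dropout weights |
|---|---|---|---|---|
| same in both arms, 20% | −0.359 | −0.342 | −0.346 | −0.357 |
| A− only, 6.25% | −0.348 | −0.302 | −0.339 | −0.348 |
| A− only, 20% | −0.348 | −0.208 | −0.318 | −0.345 |
| A− only, 30% | −0.357 | −0.159 | −0.297 | −0.354 |
| opposite, 20% | −0.352 | −0.608 | −0.432 | −0.350 |

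The weights come within 0.003 sd of full data. Baseline ACQ removes most of the bias but leaves 0.348 − 0.318 = 0.030, 0.357 − 0.297 = 0.060 and 0.432 − 0.352 = 0.080 in the last three rows.

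**Scale.** 0.02 to 0.09 sd is 0.016 to 0.072 ACQ units; 0.1 to 0.2 sd is 0.08 to 0.16 units. Against the planned A effect, 0.124/0.35 is about one third. These comparisons are approximate: the assumed variances sum to 1 for a single score, whereas the SAP's effects are in sd of change.

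**The case against.** The strongest reply is that a reader might infer that GEE fails under any MAR dropout. The documents do not support that. The covariate step in section 5.3 makes GEE valid when dropout depends only on variables in a correct mean model, and the simulation shows no bias there. The covariates are also not restricted to the baseline list, and baseline ACQ alone removes most of the bias.

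Four further inferences also go too far:
- That the GEE is unweighted. It may carry treatment-assignment weights; what is absent is dropout weights.
- That its working correlation will be near zero. None is named. Section 5.1.3 fixes only the level at which clustering is adjusted for, and quasi-least squares could supply a child-within-school structure, which nearly removes the bias for a continuous outcome.
- That the permutation test runs on raw observed means and shares the bias. Section 5.1.4 does not say so, and among its references is a paper on permutation tests with attrition weights. No commitment to those weights is made, and the test was not simulated.
- That dropout will in fact differ by arm. Nothing in the documents shows it.

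It is also fair that section 5.1 openly says the approaches rest on different assumptions, so showing disagreement is part of their purpose.

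All of this narrows the point. What stands is that, under the planned remedy, protection of the GEE depends on choices the SAP does not make, and that disagreement is uninformative if its source cannot be identified.

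**Conclusion.** The point holds as a cheap improvement, not as a demonstrated bias. The planned GEE and quasi-least-squares analyses are not generally protected under MAR. If dropout depends on earlier ACQ differently by arm, and the working correlation does not link a child's visits, the month-12 contrast can be off by about 0.02 to 0.09 sd at 6.25% loss and about 0.1 to 0.2 sd at an assumed 20%. It is near zero if the mechanism is common to both arms.

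The 6.25% treats every non-evaluable child as a lost month-12 ACQ; the protocol does not define evaluable in those terms. The 20% and 30% rates, the slopes and the mechanisms are assumptions. Dropout was varied by child-level arm only, so the size for the school contrast is untested. The mixed model's advantage assumes that its covariance is right.

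**What to change.** In SAP sections 5.1.3 and 5.3:
1. Fit the GEE and quasi-least-squares models with inverse-probability-of-observation weights from a model containing prior ACQ, arm and their interaction, multiplied by any treatment-assignment weights. Alternatively, run them on multiply imputed ACQ from a model that respects child and school levels.
2. Specify a working correlation for repeated measures on a child within school, and keep the robust variance at school level.
3. State the missing-data assumption for each approach, and the missing-outcome method for the permutation test, for example the same weights or imputations.
4. For missed visits followed by a return, say which score counts as prior (for example the last observed one) or use the imputation route.

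The cost is one dropout or imputation model and slightly wider GEE intervals. No new data and no design change are needed. The SAP is dated as final on September 13, 2022; if outcomes have already been analysed, report the weighted or imputed GEE as a labelled later addition.

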5.4 Dropout and switching

All analyses will follow the principles of "intention to treat" (as randomized) for both the school and child level randomizations (S+ vs S- and A+ vs A-). The following special rules apply for unusual situations.

(1) Child dropout or loss to follow-up

If a child leaves the study, his or her data will be captured and used until dropout. There will be no change in the A+ A- assignment.

(2) Child remains in the study but leaves a named school

If the child remains in the study but leaves a named school (cells a,b,c,d), she will be moved to the cells e or f as appropriate. This change in designation will not affect the contrast of A+ vs A-within a school designation. Data that accrues while the child is in cells a,b,c, or d will be linked to that school until the time of the switch for contrasts of S + vs S-.

After a switch from a,b,c or d, to e or f, the child-level observation will apply to the e and f cells.

(3) Child randomized while in e or f and moves into an enrolled school (cells a, b,c,d) then his or her follow-up is attributed to the e or f cell until the switch, and then to a,b,c or d cells thereafter. Both sets of longitudinal data can share the same baseline measures of outcome.

If this switch occurs, the child will be recoded separately according to the "S" allocation.

5.5 Original power estimates for planning purposes

Power calculations are for planning purposes only. The following paragraph is historical information only.

The following description and table report power calculations as originally planned for the study design. Alternative power calculations for fewer patients appear later.

All power estimates are based on custom programmed simulations. All power estimates represent changes over time in the primary outcomes (asthma control) in units of standard deviation of change. For translation into clinical terms, the minimally important difference (MID) for children on the Juniper's Asthma Control Questionnaire is 0.5 standard deviation units, which equates to 0.4 units on the questionnaire scale (for children ages 6 to 17 years). (Nguyen 2014). The power simulations assumed a modest degree of variation in outcomes across schools, which equates to clustering of children within schools. For an overall effect size of 0.5 standard deviation units, we assumed that individual schools would vary from no effect (0.0) to a large effect (1.0sd units). This degree of variation coefficient (ICC) of 0.06. With an average of 28 children per school, this variability equates to a design effect (variance inflation factor) of about 2.5. As the table shows, the contrasts for the navigator intervention are powerful to show even small effects, because they are within-cluster comparisons and therefore are influenced if at all only slightly by clustering of children within schools. Across school contrasts, of the effects of the school intervention, remain powerful for MID changes.

Specific	Contrast	Contrast	Stipula	ted		Estimated
Aim		(Table cell)	Effect size(sd)		Power	
			А	S	A,S	
1a	S+ v S-	a,b vs c,d	0.5	0.5	0.1	0.90
1a	A+ v A-	a,c vs b,d	0.25	0.25	0.1	0.95
1b	S+A+ v S-A+	a vs c	0.5	0.5	0.1	0.95
1c	S- A+ v S+A-	b vs c	0.75	0.25	0.0	0.92
1d	S+A+ v S-A-	a vs d	0.25	0.25	0.1	0.96
	S- A+ v S-A-	c vs d	0.35	0.5	0.0	0.90
	S+A- v S-A-	b vs d	0.5	0.5	0.1	0.90
20%	Subgroup					
2a	S+ v S-	a,b, vs c,d	0.5	0.6	0.1	0.83
2a	A+ v A-	a,c vs b,d	0.5	0.6	0.1	0.88

Table Y. Power for contrasts of interest.

A=Navigator effect; S=School Effect; AS= interaction; "+" = , "-" = control Cells e, f are not included in this table for simplicity and to be conservative.

6 Analysis of subgroups

Specific Aim 2: Explore moderators and mechanisms of effectiveness of the asthma navigator and school-based asthma therapy interventions.

6.1 *Heterogeneity of treatment effect -- Effect modification (moderators)*

Effect modifiers are factors that reflect differences in the effect of the intervention across subgroups of children and/or schools. When taken together these child or school level factors can describe those children or schools that are predicted to do better or worse than the reference group of schools or children. "For a clinical trial that establishes treatment efficacy in its overall population, investigating consistency of treatment effects across subgroups is important for interpreting the efficacy findings and consequently for determining the appropriate population for treatment use." (Alosh 2017) Effect modification is to be distinguished from program interaction, which in this factorial-design trial will estimate the degree to which the combination of child and school level interventions achieves synergy (or antagonism).

As subgroup analysis is fraught with problems of multiple comparisons, we shall adhere to the following principles for analysis and reporting: pre-specification of subgroups of interest, focus on subgroups that are clinically important as suggested by prior research, and attention to considerations of statistical power for identifying subgroups.

6.1.1 School level characteristics

School characteristics appear in Table 6.1a. Because the number of factors when cross classified is large (3*3*4=36) relative to the total number of schools in the sample, effect modification by school will be based on post-hoc ordering of schools by their predicted level of improvement, standardized by child characteristics. With mixed effects models that include random intercepts and slopes for school, we propose to order each school in the intervention group by its "prediction" (the combination of expected value and random effects) at both baseline and at month 12. This ordering will (a) account for measurement error in the outcome of interest (the main outcome is asthma control), (b) adjust estimates by the number of observations at the child level over time, and (c) permit consideration of both the level at baseline and the trend over time of the degree of asthma control. By contrasting for each school the change over time in predicted asthma control levels for children enrolled in the study from that school, we can identify the schools with the most improvement and the least improvement. A description of the characteristics of the high (and low) performing schools will then support conclusion (and generate hypotheses) about school-level factors related to the success (or failure) of the intervention.

Table 6.1a

School Subgroups as candidate effect modifiers	HYPOTHESIS
(1) FCI,(2) school absenteeism rate,(3) poverty level	Children going to schools with poorer FCI, higher school absenteeism rate and greater # of households living below poverty level will demonstrate the least amount of improvement with school intervention
(1) Climate,(2) leadership,(3) positive attitudes	Schools will improve more from the intervention if at baseline they have more positive climate, stronger implementation leadership, and more positive attitudes towards evidence-based practice.
 (1) Charter vs Non-charter (2) < 500 students vs > 500 students (3) Facility score Index (4) Census tract 	 H1: students who attend charter schools will achieve greater reduction of missed school days during the intervention H2: schools with lower FCI's will have more asthma triggers which will lead reduced improvement in missed school days H3: improvement in school absences from the intervention will differ based on census tract of school (effect modification by census tract)

Descriptive analysis of schools:

Charter school performance remains of special interest. For other school characteristics, we will look at the schools in order of their performance and then describe any differences. Owing to the small number of children in some of the schools, the relatively small number of schools relative to the number of school characteristics of interest, this exercise in looking for effect modification by school must inevitably be entirely exploratory and descriptive.

Statistical analysis of effect modification by charter school status.

Nevertheless, the number of children recruited from charter schools as of 12/2019 has been substantial. For that reason, we shall revisit the feasibility of comparing charter vs non-charter schools formally once total counts of evaluable schools and children are complete. Decisions about feasibility will be made before considering outcomes. (12/21/2019)

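### SAP 6.1.1 ranks intervention schools only, so a school feature that goes with improvement anywhere cannot be told apart from one that modifies the intervention effect

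*SAP*

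**What the plan says.** SAP 6.1 gives the definition: "Effect modifiers are factors that reflect differences in the effect of the intervention across subgroups of children and/or schools". SAP 6.1.1 then sets the method for school characteristics: "effect modification by school will be based on post-hoc ordering of schools by their predicted level of improvement, standardized by child characteristics". The schools ranked are those of one arm: "we propose to order each school in the intervention group by its" mixed-model prediction at baseline and at month 12. The ranked quantity is a within-school change: "By contrasting for each school the change over time in predicted asthma control levels for children enrolled in the study from that school". The most and least improved schools are then described, and that description "will then support conclusion (and generate hypotheses) about school-level factors related to the success (or failure) of the intervention".

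Two qualifications follow in the same section. Because some schools have few children and schools are few relative to the characteristics of interest, "this exercise in looking for effect modification by school must inevitably be entirely exploratory and descriptive". Charter status is set apart: "we shall revisit the feasibility of comparing charter vs non-charter schools formally" once counts are complete, with feasibility decided before outcomes are considered. The SAP does not say whether that comparison would use the S- schools.

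Control schools are used elsewhere. The mixed-model section of SAP 5.1 estimates variation in slopes over 18 intervention and 18 control schools, but does not link it to school features. SAP 6.1.2.2, under patient-level subgroups, contrasts all four treatment groups at time 0 and at the endpoint.

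**The concern.** An effect is a difference between what happens with the intervention and what would have happened without it. The month-12 change in an S+ school contains both parts. A feature common among the top-ranked S+ schools may be there because the school intervention works better in such schools, or because children in such schools improve more whatever the school receives. The ranking gives the same picture in both cases. Standardizing by child characteristics does not remove prognostic differences that sit at school level.

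Differences in background change between schools are plausible here. Children are eligible because of recent exacerbations or utilization (protocol 3.4.1), so some regression to the mean is expected. SAP 10 also allows that pandemic restrictions may shift outcomes over time. Poverty, facility condition and absenteeism (Table 6.1a) could each go with the size of such change.

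At stake is the school-level part of Aim 2a. A feature could be reported as bearing on the success of the intervention when it only marks schools that improve anyway. The reverse can also happen: a real modifier is missed because an opposite prognostic difference cancels it.

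**Working it through.** **Inputs from SAP 8.** 36 schools (18 S+, 18 S-), 12 children per school, n=432; between-school SD 0.25; residual variance 1.0; ICC 0.06; design effect 1.66; S effect 0.5 sd. Alpha is 0.05 (SAP 5.1.4), taken as two-sided because sidedness is not stated.

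**The plan's own figures first.**
- ICC = 0.0625/1.0625 = 0.059.
- Design effect = 1 + 0.06 x 11 = 1.66.
- Power for S+ v S- = Φ(0.5/√(2 x σ² x 1.66/216) − 1.96). With σ² = 1.0 this is Φ(4.03 − 1.96) = 0.981. With σ² = 1.0625 it is Φ(3.91 − 1.96) = 0.975. The SAP states 0.97, so the variance inputs reproduce.

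**Structure.** For school j with feature X, change = background + p·X in either arm, plus (0.5 + m·X) in S+ only, plus noise. Here p is the prognostic shift and m the modification. The S+ schools alone identify p + m. The S- schools identify p. Only the difference between arms identifies m.

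**Illustration 1: continuous feature, m = 0.** The correlations with the school component of change are assumed; neither document gives one. A t-test of the top six against the bottom six S+ schools stands in for the planned descriptive reading. The comparator is the S x feature term in a regression over 36 school means (32 df). There were 20,000 simulated trials per row.

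| Assumed correlation | S+ ranking flagged | S x feature flagged |
|---|---|---|
| 0.2 | 7% | 5% |
| 0.3 | 10% | 5% |
| 0.5 | 21% | 5% |
| 0.8 | 47% | 5% |

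**Illustration 2: binary feature in half the schools of each arm.** School-mean variance = 0.0625 + 1/12 = 0.146. Both analyses test the feature at p<0.05: within S+ alone, or as the difference between arms. There were 20,000 runs per row; the shifts are assumed.

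| Prognostic shift p (sd) | Modification m (sd) | S+ only flagged | Between-arm contrast flagged |
|---|---|---|---|
| 0.25 | 0 | 26% | 5% |
| 0.5 | 0 | 74% | 5% |
| 0.75 | 0 | 98% | 5% |
| −0.5 | 0.5 | 5% | 48% |
| 0 | 0.5 | 73% | 47% |
| 0 | 0.75 | 98% | 82% |

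Rows 1 to 3 show a purely prognostic feature taken for a modifier. Row 4 shows a true modifier hidden. Rows 5 and 6 show what the comparator costs in power. The standard error of the between-arm contrast is √(4 x 0.146/9) = 0.25, against √(2 x 0.146/9) = 0.18 within S+. With p = 0.5 and m = 0, on average 75% of the top half of ranked S+ schools carry the feature, where 50% would be expected of an unrelated one.

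**The case against.** The SAP does not oversell this analysis. It calls it exploratory and descriptive, speaks of generating hypotheses as well as supporting a conclusion, and predicts in SAP 9.2 that attempts to show heterogeneity will very likely fail. It plans no t-test, no split into sixes and no p-value for the ranking. If p-values were asked for, SAP 6.1.6 and 9.1(c) apply Bonferroni, which would lower the flag rates above. Its reason for ranking is that the cross-classified factors are too many for the number of schools. All this stands and limits the weight of the point. It does not remove it. The caveat is about small numbers, and more S+ schools would only make the mixture p + m more precise. Bonferroni does not correct a contrast that targets the wrong quantity. Too many crossed factors argues for one factor at a time, not for leaving out the control schools.

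A reader might infer more than the documents support:
- **That prognostic features will be mistaken for modifiers.** They cannot be told apart; how often this misleads depends on a prognostic strength that the documents do not give. At a correlation of 0.2 the excess over 5% is small.
- **That charter status is judged by this ranking.** It has its own conditional formal comparison.
- **That any secular trend distorts the ranking.** A trend shared by all S+ schools adds a constant and cannot change their order; only differences between schools in background change matter. The predictions also allow for measurement error and baseline level, which meets part of the regression-to-the-mean worry.
- **That every Table 6.1a characteristic is available in all 36 schools.** SAP 3.3 describes a selected set of schools for implementation interviews and two schools ineligible for staff surveys. SAP 6.2.8 places climate, leadership and attitudes under the implementation aim. SAP 3.1 reports a lack of facility-condition data for the third-wave charter schools.

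**Conclusion.** The point holds for school characteristics other than charter status. The ranking in SAP 6.1.1 does not estimate effect modification as SAP 6.1 defines it, because it has no comparator, and the exploratory label does not tell the reader so. The structural argument needs no assumed numbers. The size does: the flag rates of about 7% to 47%, against about 5% with control schools, rest on assumed correlations of 0.2 to 0.8, on the variance inputs of SAP 8, on equal school sizes, and on a t-test standing in for a descriptive reading. This is a minor point about one exploratory analysis under a secondary aim. It leaves the primary contrasts untouched.

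**What to change.** Amend SAP 6.1.1 as follows.

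1. Rank and describe S+ and S- schools side by side, and interpret only differences between the arms.
2. For characteristics recorded in both arms, estimate S x time x characteristic in the existing mixed model, one characteristic at a time. Report it as exploratory with a confidence interval.
3. Where a characteristic is recorded only in S+ schools, report it as associated with improvement in S+ schools, not as a modifier.
4. If the formal charter comparison goes ahead, state that it uses the S- schools too.

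The cost is wording and a few extra model terms, since the model already includes the control schools. The team must first check which Table 6.1a characteristics exist in both arms. Power will be modest (about 47% for a 0.5 sd binary modifier, 82% for 0.75 sd), so a wide interval should not be read as absence of modification.
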